11.2. DSMB

An independent Data Safety and Monitoring Board (DSMB) will be set up consisting of qualified volunteers with the necessary knowledge of clinical trials. The DSMB will receive summary reports, prior to each meeting. All data reviewed by the DSMB will be in the strictest confidence. A DSMB charter will outline its responsibilities and how it will operate.

The DSMB will meet formally at the following timepoints:

- Before the study starts
- At the end of the study (i.e. after the last patient has finished follow up)
- Unscheduled meetings can be held on the initiative of the Medical Monitor ([name], [contact]), Principal Investigator, or DSMB to consider e.g. serious adverse events as they are reported on monthly basis OR if an earlier safety review is thought to be indicated.

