Cost effectiveness of drug treatment for severe malaria is important and needs to be based on reliable evidence in the context of the high mortality caused by the disease.¹³ Previous assessments have shown that compared to parenteral quinine, AS is highly cost effective for the treatment for severe malaria in Asia and Africa.^{14,15} In the current study we will focus on the costs of the two different artesunate formulations and the consumables needed for their administration. These direct costs are important at the hospital level, but also for deployment in the wider health system. For example, for the public health system: the shipment cost for the 1-step artesunate will be cheaper than the cost for the conventional 2-step artesunate because the unit volume per pack (box) is smaller for the 1-step artesunate, and lighter.

The new formulation contains the same dose of active compound, artesunate, as the conventional formulation, and has shown bioequivalence in a comparative study in healthy subjects ([name], University of Oxford, personal communication). However, it has not been deployed, yet, for the treatment of severe malaria patients. Although not the primary goal of the study, we will accurately document efficacy, safety and tolerability outcomes using the new formulation. As an exploratory endpoint, these outcomes will be compared with the conventional artesunate formulation, since the study is not powered to compare these formally. Efficacy, safety and tolerability will be assessed through in-hospital monitoring of vital signs, physical examinations, blood smears, biochemistry assays and full blood counts. Adverse events will be recorded.¹⁶ As an important pharmacodynamic measure of the drug, parasite clearance dynamics will be assessed by repeated assessments of the parasite counts after the start of parenteral antimalarial treatment.¹⁷

The sites have been chosen based on their ability to recruit patients with severe malaria, presence of established clinical research programme, and the feasibility to perform the proposed research activities. They also represent large African countries, one French-speaking in Central Africa, and one English-speaking in East Africa, and both with a substantial burden of severe falciparum malaria. Moreover, advanced marketing authorisation has been approved in Tanzania and the DRC, and in two other countries, Malawi and The Gambia ([name], Fosun Pharma, personal communication).

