8.1 Definitions

8.1.1. Adverse Event (AE)

An AE is any undesirable event or clinical deterioration that occurs to a study participant during the course of the study; that is, from the time of administration of study drugs until study ends (i.e., until the follow up visit) whether or not that event is considered related to the study drugs, or to a concomitant drug or procedure, e.g.

- any unfavourable and unintended symptom
- physical sign
- abnormal laboratory result
- an illness
- any pre-existing condition that has worsened in grade

Any new clinical sign or clinical deterioration that occurs between signing the consent form and the administration of study drugs is not an AE. This information will be recorded in the medical records, as a pre-existing condition.

Condition associated with severe malaria

Common conditions resulting from a deterioration of severe malaria as per list should not be considered or reported as Adverse Events. They are recorded in the specific section of the CRF.

A list of the most common conditions in severe malaria includes,

- Deterioration of BCS or GCS
- Coma not present at admission
- Convulsions not present at admission
- Posturing not present at admission
- Decompensated shock (children systolic BP <70 mm Hg)
- Compensated shock (capillary refill >3sec /temperature gradient)
- Respiratory distress
- Hypoglycaemia (glucose <3 mmol/L)
- Severe anaemia
- Severe bleeding (requiring blood transfusion)
- Hemoglobinuria
- Severe jaundice
- Renal failure (urine output <0.5 mL/kg/hr >24 hours)

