8.2 Reporting Procedures for Serious Adverse Events (SAEs)/ SUSARs

All SAEs are recorded in a CRF. They need are to be reported as follows:

Safety team:

All SAEs are to be reported to Safety team (PI, Sponsor representative (CTSG), project coordinator, and medical monitor) by e-mail to [contact] within 24 hours of site awareness. If further data is required, additional documentation can be submitted, but an initial report should be submitted within the 24-hour timeframe.

SAE, including death, resulting from a deterioration of severe malaria will not follow expedited reporting (24-hour timeframe), but reported monthly.

DSMB:

All SAEs are reported to DSMB on a monthly basis

Ethics Committee and the Regulatory Authorities:

All SAEs must also be reported to the ECs and the Regulatory Authorities as per required by local guidelines

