1.5 Interim analyses

The interim reports will be upon request by the DSMB. No stopping rules both statistical as well as clinical will be specified. The need to stop the trial will be based on the perception of the accumulating data by the DSMB.

2. Study objectives and endpoints

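### First use of 1-step artesunate in severe malaria: the protocol and SAP schedule no DSMB meeting and no by-arm review of deaths, deterioration or parasite clearance during recruitment

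*Protocol*

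**What the plan says.** - **Novelty.** Protocol 3.2 states of the 1-step formulation: "However, it has not been deployed, yet, for the treatment of severe malaria patients". The same section says parasite clearance is collected as a safeguard against a large, unforeseen difference in drug action.
- **DSMB meetings.** Protocol 11.2 lists two fixed times, "Before the study starts" and "At the end of the study (i.e. after the last patient has finished follow up"). It then adds: "Unscheduled meetings can be held on the initiative of the Medical Monitor", the principal investigator or the DSMB itself. Summary reports are tied to meetings. The DSMB's working rules are left to a charter.
- **Interim data.** Under SAP 1.5 interim reports are made at the DSMB's request. "No stopping rules both statistical as well as clinical will be specified"; any decision to stop rests on the DSMB's reading of the data as they accumulate.
- **SAE reporting.** Protocol 8.2 sends SAEs to the safety team within 24 hours and all SAEs to the DSMB monthly. The exception to the 24-hour rule is: "SAE, including death, resulting from a deterioration of severe malaria will not follow expedited reporting (24-hour timeframe), but reported monthly".
- **Deterioration.** Protocol 8.1.1 says: "Common conditions resulting from a deterioration of severe malaria as per list should not be considered or reported as Adverse Events". These conditions go to a separate CRF section. SAP Table 5 nevertheless tabulates many of the same conditions by arm as graded adverse events.

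**The concern.** The protocol itself names lost drug activity as the possibility to exclude. In severe malaria that would appear as slower parasite clearance, clinical deterioration or death from malaria. The reporting rules treat these signals less urgently than other events: malaria deaths lose the 24-hour route, listed deterioration is outside adverse event reporting, and parasite data are not in any routine report to the DSMB. The trial is open-label (protocol 6.3), so the judgement that a death resulted from malaria can be made by staff who know the arm.

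Reassurance from the bioequivalence study comes from healthy volunteers. There, IV artesunate peak concentration missed the 80-125% criterion (Appendix 5, Table 1: ratio 81.50%, 90% CI 74.74 to 88.87), although dihydroartemisinin and the combined exposure met it. What is at stake is whether an unfavourable pattern between arms would be looked for while children are still being enrolled.

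**Working it through.** **1. The plan's own figure.** Margin 1 minute, SD 2 minutes, one-sided alpha 0.025, power 90% (protocol 9.1):

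n = 2 × (1.960 + 1.282)² × 2² / 1² ≈ 84.1, so 85 per arm; 85 / (1 − 0.15) = 100 per arm.

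This reproduces. It concerns preparation time only, and matters here because it sets 100 children per arm.

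**2. Exposure before the first scheduled by-arm look.** With 1:1 allocation:

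| First scheduled look | Children on 1-step by then |
|---|---|
| As written, after the last follow-up | 200 / 2 = 100 |
| Review at 100 children | 100 / 2 = 50 |
| Review at 50 children | 50 / 2 = 25 |

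Planned recruitment is 200 in 12 months: 200 / 12 = 16.7 a month, or 8.3 per arm. Waiting for day 7 adds about 16.7 × 7/30 ≈ 3.9 children, about two per arm.

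**3. Could deaths alone give the signal?** The documents give no expected overall mortality, so control mortality of 5%, 10% and 20% is assumed, doubled on 1-step. This is a stress test, not a forecast. Two-sided 5% test of two proportions:

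power = Φ{[d − 1.96 × √(2p̄(1−p̄)/n)] / √([p₁(1−p₁) + p₂(1−p₂)]/n)}, where d = p₂ − p₁ and p̄ is the mean of p₁ and p₂.

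For 10% vs 20% at n = 50: (0.100 − 1.96 × 0.0714) / 0.0707 = −0.57, power 29%.

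| Assumed mortality | 50 per arm | 100 per arm |
|---|---|---|
| 5% vs 10% | 16% | 27% |
| 10% vs 20% | 29% | 51% |
| 20% vs 40% | 59% | 88% |

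Deaths are a weak signal at this size unless mortality is high.

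**4. A continuous clearance measure.** Detectable standardised difference at 80% power: (1.960 + 0.842) × √(2/n), which is 0.56 SD at 50 per arm and 0.40 SD at 100. Films are already taken at 4, 8 and 12 hours and then serially until clearance (protocol 6.6.2), so the data exist. No comparison of arms is scheduled before the final analysis.

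**5. The reporting passages side by side.**
- Protocol 8.1.1: listed deterioration is not an adverse event.
- Protocol 8.1.2: an SAE is a kind of adverse event. Read with 8.1.1, listed deterioration cannot become an SAE.
- Protocol 8.2: SAEs resulting from malaria deterioration exist and are reported monthly.
- SAP Table 5: coma, convulsions, respiratory distress, shock, jaundice, haemoglobinuria, renal failure, bleeding and severe anaemia appear as graded adverse events.

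These cannot all be followed. A site applying 8.1.1 literally would leave non-fatal deterioration off the monthly list; a site applying 8.2 would include it.

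**The case against.** A reader might infer that the DSMB cannot meet during recruitment, that malaria deaths are hidden from it, or that deterioration can never reach it. The documents support none of these. Protocol 11.2 allows unscheduled meetings, and 8.2 gives the DSMB all SAEs monthly, roughly every eight children per arm. Malaria deaths are in that monthly flow, so the exemption delays them and does not remove them. Protocol 8.2 foresees SAEs from deterioration, so their status is contradictory, not settled as excluded. Ethics committees and regulators receive SAEs under local rules, and each child is followed by serial films and clinical review.

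A reader might also project excess deaths, for example 10 per 100 children under 10% vs 20% mortality. The documents give no basis for that. The 22.5% relative reduction against quinine in African children (protocol 3.1) implies a risk ratio of 1 / (1 − 0.225) = 1.29 for quinine: 10% becomes 12.9%, about 3 per 100. A doubling would make the new product far worse than quinine, despite the same active drug and dose and matching combined exposure. The 16-20% mortality in Appendix 4 is for cerebral malaria, whereas eligibility includes hyperparasitaemia alone.

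All of that stands, and it narrows the point. What it leaves open is that the monthly list has no stated by-arm format, denominators or parasite data, and an unscheduled meeting needs someone to notice a signal first. A difference between arms in clearance or deterioration is hard to see one patient at a time.

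**Conclusion.** The point holds in this limited form. Neither the protocol nor the SAP schedules a DSMB meeting or by-arm review of deaths, deterioration or parasite clearance during recruitment, and the rules on reporting deterioration contradict one another. The size is the number of children exposed before the first scheduled comparison: about 100 on 1-step, against about 50 or 25 with a review. This assumes even allocation and, for the timing, recruitment at the planned rate. No figure for excess deaths should be attached.

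The conclusion covers the protocol and SAP only. The DSMB charter and the safety monitoring plan mentioned in protocol 8.3.1 were not available and may add reviews. This is a worthwhile, inexpensive safety improvement; it does not undermine the co-primary comparisons, and no change in sample size follows.

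**What to change.** 1. **Protocol 11.2 and SAP 1.5.** Schedule at least one closed by-arm DSMB review during recruitment, for example after about 100 children reach day 7 and optionally also after about 50. With denominators, report deaths, the conditions listed in 8.1.1 from their CRF section, and early parasite reduction. Leave out preparation times and costs, so that the co-primary tests are untouched and no alpha is spent. If the charter already provides this, cite it in 11.2.
2. **Protocol 8.2.** Notify every death to the safety team within 24 hours, whatever the attributed cause.
3. **Protocol 8.1.1, 8.1.2, 8.2 and SAP Table 5.** Reconcile them, so that it is clear whether listed deterioration is an adverse event, whether it can be an SAE, and how it reaches the DSMB.

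The cost is one or two short DSMB meetings, a closed report from data already collected, and faster death notifications. The number of notifications depends on mortality, which the documents do not give: at an assumed overall 5%, 10% or 20%, 200 children would yield 10, 20 or 40 deaths, about 0.8, 1.7 or 3.3 a month.

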12. ETHICS

12.1. Declaration of Helsinki

The Investigator will ensure that this study is conducted in compliance with the current revision of the Declaration of Helsinki (Fortaleza 2013).

12.2. ICH Guidelines for Good Clinical Practice

The Investigator will ensure that this study is conducted according to any National Regulations and that it will follow the principles of the ICH Guidelines for Good Clinical Practice.

12.3. Approvals

The study protocol and its associated documents will be submitted to the Oxford Tropical Research Ethics Committee (OxTREC) and the appropriate local ethics committees for written approval.

The Investigator will submit and, where necessary, obtain approval from the above parties for all substantial amendments to the original approved documents.

12.4. Risks

Part 1:

This study will use drugs that have been studied thoroughly and their toxicities are well described. In general, they are all well tolerated.

12.4.1. Risks of parenteral artesunate

One of the concerns about the artemisinin derivatives is neurotoxicity, in particular involving the brain stem²⁴. Nevertheless, a discrepancy seems to prevail with regard to the toxicity and safety of the artemisinin family of antimalarials. While these compounds have been found to be virtually void of any serious side effects in humans, their neurotoxicity in animal models has raised concerns about their use^{25,26}. The prolonged presence of artemisinins upon slow release from oil-based intramuscular formulations at several orders of magnitude above the therapeutic level appear to be the main cause of the observed toxicity in laboratory animals.

Artesunate is rapidly and extensively converted to dihydroartemisinin (DHA), the active metabolite, primarily by plasma and erythrocyte esterases. DHA elimination from the blood compartment is also rapid (half-life approximately 45 min). The potential for drug-drug interactions with other medicinal products is limited. *In vitro* drug-interaction studies have demonstrated minimal effects of artesunate on cytochrome P450 isoenzymes. In the limited number of clinical drug-drug interaction studies that have been performed, however, no clinically significant drug-drug interactions have been identified.

Delayed haemolytic anaemia following treatment with injectable artesunate has been observed in children in malaria endemic areas and in non-immune travellers presenting with severe falciparum malaria.²⁷ The risk was most pronounced in patients with hyper-parasitaemia and in younger children. Some cases have been severe and required blood transfusion. The risk of post-artesunate delayed haemolytic anaemia has been reported however to be very low in children in highly endemic settings (Mozambique and DRC) and statistically not different from intravenous quinine¹⁸. Vigilance for delayed onset anaemia is therefore advised, particularly in hyper-parasitaemic patients and younger children, and prolonged follow-up should be considered (e.g. 14-28 days). As the overall benefit-risk ratio remains highly favourable for injectable artesunate in the treatment of severe malaria, WHO strongly recommends its continued use.

The most important reported side effect of artesunate is a rare severe allergic reaction (estimated risk approximately 1 in 3000 patients), which can present as an urticarial rash or more severe allergic symptoms, including hypotension, pruritus, oedema, and/or dyspnoea. More common minor side effects described in association with parenteral administration of artesunate include dizziness, light-headedness, rash, and taste alteration (metallic/ bitter taste). Nausea, vomiting, anorexia and diarrhoea have also been reported, however it is uncertain whether these are attributable to the drug or to the disease severe malaria.

12.4.2. Risk of phlebotomy, venepuncture, finger stick

The primary risks of phlebotomy include local discomfort, occasional bleeding or bruising of the skin at the site of needle puncture, and rarely haematoma or infection.

Part 2:

12.4.3. Risks to participation in social science studies

Some participants may feel uncomfortable by the details they have to think through during the interview. If the interviewer notices any inconvenience or distress, can divert the topic and ask if participant is comfortable for further discussion. However, we will ensure that participants are informed of their freedom not to answer questions. In addition, we will provide mechanisms to ensure responses are confidential when requested or needed. If in case interview goes longer than planned (e.g. more than 45 minutes), interviewer will remind the respondent and ask if he/she is comfortable to continue beyond the designated time.

12.5. Benefits

Part 1:

Severe malaria is a disease that needs to be treated promptly. All patients will benefit from receiving efficacious treatment at no cost. They will be followed up closely and will be given rescue treatment if clinically indicated.

Part 2:

There are no direct benefits to the participants other than their perspectives will contribute to the evidence-generation, specifically about acceptability, and practicalities related to the treatment of severe malaria using 1-step versus 2-step artesunate injections. The feasibility, acceptability and practicalities will help inform the treatment guidelines for severe malaria.

12.6. Alternatives to Study Participation

Patients or their parent/guardian can freely decline participation in this study. If so, they will receive standard care for their malaria.

12.7. Incentives & Compensation

Part 1:

The study will pay for food during hospitalization for the patients and the caregivers, and small benefits such as insecticide treated nets and soap, plus local transport costs for the follow-up visits. Any additional reimbursement and the amount in monetary terms (e.g. for the time lost from work as a result of hospitalisation) will be at the instruction of the national ethics committees. We anticipate that these are not allowed in the DRC as they are considered coercive. The study will pay locally appropriate costs for treatment of drug-related SAEs or other research-related injuries. Although the study cannot pay for long term care for disability after hospital discharge resulting from complications

of the illness the study will pay the reasonable costs for treatment of such sequelae during the follow up assessments for 12 months.

Part 2:

Appropriate reimbursement will be provided to all the participants based on the valid invoices of their travel costs.

12.8. Confidentiality

The trial staff will ensure that the participants' anonymity is maintained. The participants will be identified only a unique participant number on the CRF and the MACRO EDC database. All documents will be stored securely and be accessible to trial staff and authorised personnel only. The study will comply with the Data Protection Act 2018, which requires that personal data must not be kept as identifiable data for longer than necessary for the purposes concerned.

13. SAMPLE MANAGEMENT

Samples collected will be used for the purpose of this study as stated in the protocol.

14. DATA HANDLING AND RECORD KEEPING

Part 1:

Study data will be recorded on standard Case Report Forms (CRF) and entered to MACRO EDC[®], a GCP-compliant data management system. The database is password-protected and includes internal quality checks to identify data that appear inconsistent, incomplete, or inaccurate.

Study participants will be identified by a unique participant number in the database. The study data management plan outlines all activities that will be carried out to ensure security and quality of the data.

Subject records at site will, taking into account the ability of the sites, be stored in binders or scanned and stored electronically. The records will be retained until the youngest child participating in the trial reaches 21 or five years following completion of the study, whichever is longer. The study database will be retained indefinitely.

Participant's data and results from blood analyses stored in the database may be shared according to the terms defined in the MORU data sharing policy with data repositories or other researchers to use in the future. All personal information will be de-identified so that no individual can be identified from their treatment records, through interviews.

Part 2:

All data collected during the interviews in addition to the written informed consent will be stored at password protected principal interviewer's official computer (laptop) and an external hard drive until the end of the study. All data will be provided with a unique code that will link the personal data with the research data and will be kept separately from the research data. Research data will not have personal identifiers (e.g. name). Personal data such as their age, profession and workplace will be anonymized from the transcripts and immediately transferred and backed-up to a secure server at MORU. The audio-recordings (with personal identifiers) will be deleted after the end of the study. Duration of storage of transcripts will be guided by the MORU's data access policy. The study will comply with the General Data Protection Regulation (GDPR), which requires that personal data must not be kept as identifiable data for longer than necessary for the purposes concerned which is approximately 5 years after study completion.

